#### 11.1.1 Overview of Clinical Findings and side effects

According to the Investigator's Brochure (v. 8.0, 13-Mar-2017), skin toxicities were the most frequently reported AEs. To date (20 Jan 2017), approximately 380 subjects with solid tumors, including subjects with recurrent/metastatic SCCHN, mCRC, ESCC and NSCLC, have been treated with Sym004 in weekly

doses of up to 12 mg/kg and in doses every other week of up to 18 mg/kg in ongoing Symphogen-sponsored studies. Anti-EGFR related skin toxicities (including rash, pruritus, skin fissures, dry skin, erythema, and paronychia) have been observed in more than 90% of subjects in the completed and ongoing clinical trials. In subjects who had previously received anti-EGFR mAb therapy, Grade 3 skin toxicities were frequently reported; 50-69% of subjects at a dose of 9 or 12 mg/kg weekly (Sym004-01 Parts B and C and Sym004-02) and 33.3% and 41.2% of subjects at dose levels of 12 mg/kg and 18 mg/kg, respectively, every other week (Sym004-01 Parts D and E).

Other adverse events (AEs) associated with anti-EGFR mAbs, such as electrolyte disturbances (in particular hypomagnesemia), mucositis, and diarrhea were also frequently observed in the completed and ongoing trials. In clinical trials for which AE data are available (Sym004-01-Parts A, B, C, D, E, Sym004-02, and EMR 200637-001-Part A), hypomagnesemia was reported in 54-77% of subjects, and 0-38% of subjects experienced Grade 3 or 4 hypomagnesemia. In the Sym004-01 and Sym004-02 clinical trials, events of hypomagnesemia also represented the majority of serious adverse events (SAEs) that were considered to be related to Sym004 therapy. Serious clinical complications of hypomagnesemia have not been observed. Mucositis was observed in up to 40% of subjects, but the number of subjects experiencing Grade 3 mucositis was low (1 subject). Diarrhea has been reported in up to 59% of subjects; and ≤ 10% of subjects experienced Grade 3 diarrhea. Infusion related reactions have also been observed.

The expected adverse drug reactions are related to the biological mode of action of Sym004 through internalization and degradation of the EGFR receptor and to infusion of a foreign protein agent (infusion-related reactions).

At a minimum, the following relevant categories of adverse drug reactions are expected to occur in relation to administration of Sym004:

- Electrolyte imbalances, including hypomagnesaemia, hypocalcemia and hypokalemia (early and aggressive replacement therapy of magnesium is emphasized)
- Dermatological toxicities, acneiform rash, skin drying and fissuring, and secondary infections. Prophylactic treatment is allowed.
- Infusion reactions of variable severity, requiring medical intervention and potential discontinuation
- Other adverse drug reactions cannot be excluded. Therefore, the patients must be closely monitored and Sym004 should be administered in an environment where full resuscitation facilities are available.

### 11.1.2 Reporting of AEs

Syphogen Global Pharmacovigilance will be provided via secure email with AE listings as appropriate, in order for analysis to be performed for the Syphogen Development Safety Update Report (DSUR) (after Data Lock Point [DLP] for the report on January 20th).

## 11.2 Serious Adverse Events

An AE is considered “serious,” if in the opinion of the investigator, it results in one of the following outcomes:

- Fatal
- Life-threatening
- Constitutes a congenital anomaly or birth defect
- A medically significant condition (defined as an event that compromises subject safety or may require medical or surgical intervention to prevent one of the three outcomes above).
- Requires inpatient hospitalization or prolongation of existing hospitalization
- Results in persistent or significant incapacity or substantial disruption to conduct normal life functions.

### 11.2.1 Reporting of SAEs to Duke Cancer Institute Safety Desk

Adverse events that are serious and unexpected are considered reportable. Reportable events that occur during the study, beginning at the time of first study drug treatment infusion) to within 30 days following cessation of study drug treatment are reportable.

The study team will complete the DCI SAE Report Form and the DCI Safety Review Form, which will both be submitted to the DCI Safety Desk ([contact] or secure email to [[contact]](mailto:[contact])) and to the PI, [name], MD, FRCPC (email: [[contact]](mailto:[contact])) or her designee within 24 hours of knowledge of the event.

The initial report for each SAE should include at minimum the following information:

- protocol # and title
- patient initials, study identification number, sex, age or date of birth
- date the event occurred
- description of the SAE
- dose level and cycle number at the time the SAE occurred
- description of the patient's condition
- indication whether the patient remains on study
- causality or causal relationship

The DCI Safety Desk will track individual SAE reports into their internal tracking database and complete the initial processing within 2 business days of receipt. For unanticipated study-related event(s), these will be processed within 1 business day of receipt.

De-identified source documentation (i.e. admission notes, discharge notes, applicable laboratory results, radiology/diagnostic testing results, etc.) should be sent with the SAE Report Form, if available at the time of the report. Any follow-up information including severity, action taken, concomitant medications, and outcome should be communicated to the DCI Safety Desk, as soon as possible using the same forms mentioned above. The study team should keep a copy of the initial SAE forms submitted to the DCI safety desk and any SAE follow up forms for reference.

The DCI Safety Desk will use the information provided in the DCI SAE Report Form and the DCI Safety Review Form to complete a FDA Form 3500A, and will submit it to the Duke University IRB, if it meets Duke IRB reporting requirements (see below).

Only adverse events that the Duke Sponsor-Investigator determines to be serious, unanticipated, and related or possibly/probably (i.e. more likely than not) related to the research must be reported to the Duke IRB. Those adverse events will be submitted in the electronic IRB (eIRB) system, according the following guidelines:

- Report within 24 hours of learning about any subject's death that was unanticipated and more likely related to the research than unrelated;
- Report within 5 business days of learning about any serious, unanticipated, and related or possibly/probably related adverse event;
- Report within 10 business day of learning about any other unanticipated problem or event that was more likely related to the research than unrelated.
- The Sponsor-Investigator must report to the FDA, in an IND safety report, any suspected adverse reaction that is both serious and unexpected. Before submitting this report, the sponsor needs to ensure that the event meets all three of the definitions contained in the requirement:
  - Suspected adverse reaction (i.e. there is a reasonable possibility that the drug caused the adverse event)
  - Serious
  - Unexpected

If the adverse event does not meet all three of the definitions, it should not be submitted as an expedited IND safety report.

### **11.2.2 Reporting to the FDA**

All SAE's that are possibly/probably related (i.e. there is evidence to suggest a causal relationship) and unexpected must be reported to the FDA as IND Safety Reports. The Sponsor-Investigator is required to report to the FDA all IND Safety reports in writing within 15 days (7 days for unexpected fatal or life-threatening suspected (possibly/probably related) adverse reactions) per 21CFR312.32.

The FDA Form 3500A can be found on the FDA website, [www.fda.gov](http://www.fda.gov). All other adverse events will be reported to the FDA in the Annual Report.

This will be done by the study team in cooperation with the DCI Safety Desk.

### **11.2.3 Safety Reporting to Symphogen Global Pharmacovigilance**

The Investigator shall have full responsibility for the scientific, medical and legal/regulatory conduct of the trial, as well as for study documentation and safety reporting responsibilities. The Investigator shall promptly report to Symphogen all safety-related information obtained from the study as follows:

For all expedited SAE reports (Initial or Follow-up) and any death (regardless of causality) that occurs while a subject is on study, i.e. within 30 days of the last study drug administration, regardless of any opinion as to the relationship of the SAE to the study drug, Symphogen Global Pharmacovigilance must be notified by telephone, fax, or secure email within 2 business days of the PI or designee first becoming aware of the event and the study team notifying the DCI safety desk of the event. Any urgent safety issue or communication with FDA concerning such issue should be made known to Symphogen within 24 hours of the PI or designee first becoming aware of the event and the study team notifying the DCI safety desk of the event.

All SAEs require that a Serious Adverse Event Report Form (either DCI Safety Desk SAE Report and Safety Review Forms or a MedWatch Form 3500A) be completed and forwarded to Symphogen either via fax transmission or secure email. The SAE Form must include a description narrative, inclusive of the investigator's causality assessment.

All non-expedited serious adverse events (SAEs) will be forwarded to Symphogen Pharmacovigilance within 7 calendar days of first knowledge of the event by secure email or fax transmission.

Any request by Symphogen for safety data that would need to be incorporated into the DSUR generated by Symphogen for its reporting purposes will be provided in a timely fashion, in order for Symphogen to meet its reporting timelines.

### **11.2.4 Exposure in Utero**

While reports of pregnancy are not considered SAEs, these events will be tracked for follow-up purposes and assessing outcome in the infant. If any trial subject or the female partner of a male trial subject becomes pregnant during the time of receiving study drug, or is found to be pregnant within 90 days of

the last dose of study drug, Symphogen will be notified by the DCI Safety Desk within 1 business day of the DCI Safety Desk learning of the event via fax or email and a Pregnancy Reporting Form will need to be completed. The pregnancy will be followed to term and all pregnancy information will be tracked within the Symphogen safety database.

### **11.3 Emergency Unblinding of Investigational Treatment**

Not applicable.

### **11.4 Other Reportable Information**

Not applicable.

### **11.5 Special Warnings and Precautions**

Not applicable.

### **11.6 Safety Oversight Committee (SOC)**

The Duke Cancer Institute SOC is responsible for annual data and safety monitoring of DUHS sponsor-investigator phase 1 and 2, therapeutic interventional studies that do not have an independent Data Safety Monitoring Board (DSMB). The primary focus of the SOC is review of safety data, toxicities and new information that may affect subject safety or efficacy. Annual safety reviews include but may not be limited to review of safety data, enrollment status, stopping rules if applicable, accrual, toxicities, reference literature, and interim analyses as provided by the sponsor-investigator. The SOC in concert with the DCI Monitoring Team (see Section 12.1 for Monitoring Team description) oversees the conduct of DUHS cancer-related, sponsor-investigator greater-than-minimal-risk intervention studies that do not have an external monitoring plan, ensuring subject safety and that the protocol is conducted, recorded and reported in accordance with the protocol, standing operating procedures (SOPs), Good Clinical Practice (GCP), and applicable regulatory requirements.

### **11.7 External Data and Safety Monitoring Board (DSMB)**

Not applicable.

## **12 QUALITY CONTROL AND QUALITY ASSURANCE**

### **12.1 Monitoring**

The Duke Cancer Institute (DCI) Monitoring Team will conduct monitoring visits to ensure subject safety and to ensure that the protocol is conducted, recorded, and reported in accordance with the protocol, standard operating procedures, good clinical practice, and applicable regulatory requirements. As specified in the DCI Data and Safety Monitoring Plan, the DCI Monitoring Team will conduct routine monitoring after the third subject is enrolled, followed by annual monitoring of 1 – 3 subjects until the study is closed to enrollment and subjects are no longer receiving study interventions that are more than minimal risk. Monitoring additional to the standard practice of the DCI may occur as per contractual agreement with Symphogen.

Additional monitoring may be prompted by findings from monitoring visits, unexpected frequency of serious and/or unexpected toxicities, or other concerns and may be initiated upon request of DUHS and DCI leadership, the DCI Cancer Protocol Committee, the Safety Oversight Committee (SOC), the sponsor, the Principal Investigator, or the IRB. All study documents must be made available upon request to the DCI Monitoring Team and other authorized regulatory authorities, including but not limited to the National Institute of Health, National Cancer Institute, and the FDA. Every reasonable effort will be made to maintain confidentiality during study monitoring.

### **12.2 Audits**

The Duke School of Medicine Office of Audit, Risk, and Compliance (OARC) office may conduct confidential audits to evaluate compliance with the protocol and the principles of GCP. The PI agrees to allow the OARC and

auditor(s) direct access to all relevant documents and to allocate his/her time and the time of the study team to the auditor(s) in order to discuss findings and any relevant issues.

OARC audits are designed to protect the rights and well-being of human research subjects. Audits may be routine or directed (for cause). Routine audits are selected based upon risk metrics generally geared towards high subject enrollment, studies with limited oversight or monitoring, Investigator initiated Investigational Drugs or Devices, federally-funded studies, high degree of risk (based upon adverse events, type of study, or vulnerable populations), Phase I studies, or studies that involve Medicare populations. Directed audits occur at the directive of the IRB or an authorized Institutional Official.

OARC audits examine research studies/clinical trials methodology, processes and systems to assess whether the research is conducted according to the protocol approved by the DUHS IRB. The primary purpose of the audit/review is to verify that the standards for safety of human subjects in clinical trials and the quality of data produced by the clinical trial research are met. The audit/review will serve as a quality assurance measure, internal to the institution. Additional goals of such audits are to detect both random and systemic errors occurring during the conduct of clinical research and to emphasize "best practices" in the research/clinical trials environment.

## **12.3 Data Management and Processing**

### **12.3.1 Case Report Forms (CRFs)**

The electronic CRF (eCRF) will be the primary data collection document for the study. The CRFs will be updated in a timely manner following acquisition of new source data. Only approved study staff (the PI, the research coordinators, the research nurses, the data management team, and the clinical trials manager) are permitted to make entries, changes, or corrections in the CRF.

An audit trail will be maintained automatically by the electronic CRF management system, which will be a 21 CFR Part 11 compliant database. All users of this system will complete user training, as required or appropriate per DCI requirements and other regulations.

### **12.3.2 Data Management Procedures and Data Verification**

Designated personnel using the electronic CRF will have access based on their specific roles in the protocol.

Completeness of entered data will be checked automatically by the eCRF system, and users will be alerted to the presence of data inconsistencies. Additionally, the data management team and the statistical team will cross-reference the data to verify accuracy. Missing or implausible data will be highlighted for the PI requiring appropriate responses (i.e. confirmation of data, correction of data, completion or confirmation that data is not available, etc.).

The database will be reviewed and discussed prior to database closure, and will be closed only after resolution of all remaining queries. An audit trail will be kept of all subsequent changes to the data.

### **12.3.3 Study Closure**

Following completion of the studies, the PI will be responsible for ensuring the following activities:

- Data clarification and/or resolution
- Accounting, reconciliation, and destruction/return of used and unused study drugs
- Review of site study records for completeness
- Shipment of all remaining laboratory samples to the designated laboratories

## 13 STATISTICAL METHODS AND DATA ANALYSIS

All statistical analysis will be performed under the direction of the statistician designated in key personnel. Any data analysis carried out independently by the PI must be approved by the statistician before publication or presentation.

With Amendment 31, the study has been modified to allow the assessment of activity of two different doses of Sym004: 18 mg/kg and 24 mg/kg. With the increase to 24 mg/kg dose, we intend to treat 65 additional subjects at that dose level (36 in Cohort 1, and 29 in Cohort 2). The maximum accrual goal for this study is the number of subjects accrued before Amendment 31 plus 65 more.

### 13.1 Analysis Sets

Safety and efficacy analyses will include all patients who received any Sym004 treatment.

### 13.2 Patient Demographics and Other Baseline Characteristics

Socio-demographic and clinical characteristics of patients enrolled onto this study will be summarized by study cohort and dose level. For categorical variables, frequencies and percentages will be provided. Means with standard deviations or medians/percentiles will summarize non-categorical variables.

### 13.3 Treatments

Within each cohort and dose level, a frequency distribution will be generated for the number of doses of Sym004 administered. In addition, the frequency of dose reduction will also be tabulated.

### 13.4 Primary Objective

The primary objective of the study is to assess the activity of Sym004 within two cohorts of patients with recurrent glioblastoma based upon PFS6: patients who are non-bevacizumab failures (Cohort 1) and patients who have previously failed bevacizumab (Cohort 2). This assessment will be done at both dose levels.

#### 13.4.1 Variable

The primary endpoint is PFS6, which is defined as the proportion of patients who remain alive and progression-free 6 months after initiation of Sym004 treatment. The use of PFS6 as an endpoint in phase II clinical trials is recommended by Ballman (2007) and Lamborn (2008) given the strong association between progression-free survival status and overall.

#### 13.4.2 Statistical Hypothesis, Model, and Method of Analysis

Based upon the Kaplan-Meier estimator, the proportion of patients who are alive and progression-free 6 months after initiation of Sym004 treatment will be estimated. Details about the hypothesis test that will be conducted is provided in Section 13.8.

The primary analyses will focus on the dose group to which the patient was originally assigned. No more than 2 of the patients treated initially at the 18 mg/kg dose will have their dose escalated to 24 mg/kg. Efficacy analyses will be generated with and without these patients to assess the impact of these patients with dose escalation on inferences.

#### 13.4.3 Handling of missing values, censoring, and discontinuations

The sample size justification provided in Section 13.8 assumes that all patients will be followed for their clinical status for at least 6 months or until death. Historical data within the Preston Robert Tisch Brain Tumor Center suggests that such an assumption is fully achievable. If patients are lost to follow-up prior to their 6-month outcome, estimates of PFS6 will be appropriately adjusted for such censoring in the estimation of the outcome from the Kaplan-Meier estimator.

## 13.5 Secondary Objectives

Secondary objectives are to determine the safety of Sym004 in recurrent GBM patients and to determine response rate (RR) and overall survival (OS) in recurrent GBM patients. These analyses will be generated for both dose levels.

### 13.5.1 Key Secondary Objective: Safety

Within each cohort and dose level, the proportion of patients who experience grade 3, 4, or 5 adverse events that are possibly, probably, and definitely related to protocol treatment will be estimated.

In addition, for each type of toxicity, the maximum grade experienced by each patient will be summarized with frequency distributions. Two adverse experience tabulations will be generated, one that includes all toxicities regardless of attribution, and one that includes only toxicities that are possible, probably, and definitely related to Sym004 treatment.

Patients who have their dose escalated from 18 mg/kg to 24 mg/kg will be included in toxicity summaries for 18 mg/kg and 24 mg/kg. The toxicity experienced prior to dose escalation will be summarized with the other patients treated at the 18 mg/kg dose level; whereas, the toxicity experienced after dose escalation will be included in the summary of adverse events associated with 24 mg/kg.

### 13.5.2 Other Secondary Objectives: Response Rate and Survival

Within each cohort and dose level, radiographic response rate will be estimated as the proportion of treated patients with a complete or partial response. An exact binomial confidence interval will be generated.

Kaplan-Meier curves will be generated to describe the PFS and OS experience of patients treated with Sym004 within each cohort and dose level. Progression-free survival (PFS) is defined as the time interval between initiation of protocol treatment and either disease progression or death. If the patient is alive and progression-free, PFS will be censored at the date last known alive. Overall survival (OS) is defined as the time interval between initiation of protocol treatment and death, or date of last follow-up if alive. Estimates with confidence intervals will be generated for median PFS/OS, as well as 2 month intervals for PFS for the first year (2, 4, 6, etc..) and 6 month intervals for OS for the first 2 years (6,12, 18, 24) from the time the subject goes on study.

The analyses of response rate, OS, and PFS will focus on the dose group to which the patient was originally assigned. The impact that the few patients treated initially at the 18 mg/kg dose and subsequently with 24 mg/kg will be assessed by generating analyses with and without these patients.

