#### 7.1.1 Dose Modification

For subjects receiving 18 mg/kg, the dose of Sym004 may be reduced by up to two dose levels, if the subject experiences grade 3-4 non-hematologic toxicities secondary to Sym004, e.g. skin toxicities, electrolyte disturbances, and gastrointestinal symptoms, or grade 4 neutropenia or thrombocytopenia. Following the initial dose of 18 mg/kg every 2 weeks, if the subject needs to have their dose of Sym004 reduced due to an aforementioned toxicity, then their next dose will be 15 mg/kg every 2 weeks. If another reduction in dose is necessary, the subsequent dose will be 12 mg/kg every 2 weeks. If dose reduction is required more than two times, the patient will be removed from the study.

#### 7.1.2 Dose Modification Post-Amendment 31

For subjects receiving 24 mg/kg, the dose of Sym004 may be reduced by up to two dose levels, if the subject experiences grade 3-4 non-hematologic toxicities secondary to Sym004, e.g. skin toxicities, electrolyte disturbances, and gastrointestinal symptoms, infusion-related reactions, or grade 4 neutropenia or thrombocytopenia. Exceptions to this dose reduction include grade 3 nausea, vomiting, diarrhea or fatigue lasting  $\leq$  5 days with supportive care or grade 3 asymptomatic electrolyte abnormalities. Following the initial dose of 24 mg/kg every 2 weeks, if the subject needs to have their dose of Sym004 reduced due to an aforementioned toxicity, then their next dose will be 18 mg/kg every 2 weeks. If another reduction in dose is necessary, the subsequent dose will be 15 mg/kg every 2 weeks. If dose reduction is required more than two times, the patient will be removed from the study.

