## 7.3 Definition of Evaluable Subjects, On Study, and End of Study

Safety and efficacy analyses will include all patients who received any Sym004 treatment.

Patients will be considered "on study" once they have signed the informed consent form, and will continue to be considered "on study" as long as they are receiving study-related treatment or are undergoing study-related follow-up tests and procedures. If a patient who signs the informed consent form does not meet the eligibility criteria of the study, he or she will come off study as a "screen failure." Patients who sign informed consent, are eligible to participate, and receive study-related treatment are considered enrolled in the study. Subjects will be considered "off study" when they are no longer receiving study-related treatment and are no longer having study-related follow-up tests and procedures. Once "off study," subjects who are not screen failures will be followed for progression (for patients who came off study prior to disease progression) and survival status (all patients) for at least 1 year, if possible.

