## 10.5 End of Treatment

The End of Treatment visit, i.e. the date of a subject's last treatment visit, should include:

- Interval history and full physical exam, including a full neurologic assessment and KPS
- Vital signs, including blood pressure and weight
- Hematology including CBC/differential
- CMP + Mg
- MRI of the brain
- Quality of life measurements (should be performed prior to other study-related evaluations at study visits, if at all possible)
- Skin toxicity assessment
- Toxicity assessment

If a subject goes off study and does not return to clinic as part of a regular study visit, not all tests listed above may be obtained as part of end of treatment, e.g. magnesium. If this occurs, only the assessments that are reasonably obtainable will be collected as part of end of treatment.

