## 10.6 Follow-up Period

Patients will be followed for safety a minimum of 30 days after last dose of study drug, and also followed for any new and/or unresolved serious adverse events considered related to study therapy. Once "off study," subjects will be followed for progression (for patients who came off study prior to disease progression) and survival status (all patients) at least 1 year, if possible. Subjects not returning to Duke will be contacted via phone or information will be obtained through their local physician every 3 months to determine time of progression or survival.

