### **10.8.2 Follow-up Requirements for Early Withdrawal**

If an enrolled subject withdraws from the study prematurely, they will be asked to complete the tests/procedures that would have been conducted at their next scheduled visit, if physically possible. Patients will be followed for a minimum of 30 days after last dose of study drug, and also followed for any new and/or unresolved serious adverse events considered related to study therapy.

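### PFS is censored at the date last known alive, and no other date is given for the primary Kaplan-Meier PFS6, so unassessed time can count as progression-free in the reported estimate

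*Combined protocol and SAP*

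**What the plan says.** **Censoring rule.** Section 13.5.2 says "If the patient is alive and progression-free, PFS will be censored at the date last known alive". Section 3.4 has the same sentence. No section censors PFS at the last MRI or the last disease assessment.

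**Primary estimate.** Section 13.4.2 says "Based upon the Kaplan-Meier estimator, the proportion of patients who are alive and progression-free 6 months after initiation of Sym004 treatment will be estimated". For patients lost before their 6-month outcome, section 13.4.3 says "estimates of PFS6 will be appropriately adjusted for such censoring in the estimation of the outcome from the Kaplan-Meier estimator". Neither section names a date.

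**Decision rules.** Section 13.4.2 refers the hypothesis test to section 13.8. Sections 13.7.2, 13.8.1 and 13.8.2 decide by the number of patients who live 6 months progression-free.

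**Assessment on treatment.** MRI is every 8 weeks (section 10). If toxicity delays dosing by more than 2 weeks, section 10.4 still requires the MRI no later than 8 ± 2 weeks after the previous one.

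**Leaving treatment without progression.** Sections 7.1.1 and 7.1.2 both say "If dose reduction is required more than two times, the patient will be removed from the study". Section 10.8.1 also lists intolerable symptoms and the patient's own request.

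**Assessment afterwards.** Sections 7.3 and 10.6 ask for follow-up for progression for at least 1 year, as far as possible. For patients who do not return, there is phone contact or "information will be obtained through their local physician every 3 months to determine time of progression or survival". No off-study scan schedule is given. Section 10.5 includes an End of Treatment MRI but accepts that "not all tests listed above may be obtained as part of end of treatment" when the patient does not return for a regular visit. For early withdrawals, section 10.8.2 says that "they will be asked to complete the tests/procedures that would have been conducted at their next scheduled visit, if physically possible".

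**The concern.** Knowing that a patient is alive does not show that the patient is free of progression. The date last known alive is the right censoring date for OS. Used for PFS, it keeps a patient in the progression-free risk set through time when nobody looked for progression. Later events are then divided by too large a risk set, and the patient can still stand as progression-free at 6 months. The error from this mechanism favours the drug.

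PFS6 is the primary endpoint of an uncontrolled study, so no comparator arm followed under the same rule could offset a shift. Its estimate and interval will be read beside the 20% and 3% reference rates. The documents do not give the censoring rules behind those rates, so offsetting cannot be checked. Cohort 2 is the more sensitive: one patient is 1/29 = 3.4%, about the size of its 3% null.

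**Working it through.** **1. The plan's own figures.** Exact enumeration of the Cohort 1 design (more than 3 of 19 to continue, more than 10 of 36 to succeed) gives type I error 0.0861, type II error 0.0976, expected sample size 28.26 and early-termination probability 0.4551. This matches section 13.8.2 (0.086, 0.098, 28.26, 0.455). The design works on counts alone, and no Kaplan-Meier quantity enters it.

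**2. Effect of one patient.** Take a patient last scanned at week 8 without progression, never scanned again and known alive at 6 months. With 8-weekly scans, the last scan before week 26 is at week 24. Under a constant hazard, the difference between last-known-alive and last-assessment censoring is

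shift = (1/n) × (1 − S(24)/S(8)), with S(8) = S(24)^(1/3).

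- Cohort 1: S(24) = 0.20, S(8) = 0.585, ratio 0.342. Shift = 0.658/36 = 1.83 points.
- Cohort 2: S(24) = 0.03, S(8) = 0.311, ratio 0.097. Shift = 0.903/29 = 3.12 points.

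**3. Worked Kaplan-Meier examples, each with one such patient (illustrative data).**

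- n = 36, with 15, 8 and 5 progressions at weeks 8, 16 and 24, and 7 patients progression-free.
  - Last known alive: 21/36 × 13/21 × 8/13 = 22.2%.
  - Last assessment: 21/36 × 12/20 × 7/12 = 20.4%.
  - Counted as failure: 7/36 = 19.4%.
- n = 29, with 19, 6 and 2 progressions at the same weeks, and 1 patient progression-free.
  - Last known alive: 10/29 × 4/10 × 2/4 = 6.9%.
  - Last assessment: 10/29 × 3/9 × 1/3 = 3.8%.
  - Counted as failure: 1/29 = 3.4%.

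**4. Expected bias under stated assumptions.** The documents give no missed-scan rate and no capture rate, so both are assumed. The simulation used 600,000 patients per scenario and the following inputs:

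- exponential progression, calibrated to a fully scanned PFS6 of 20% or 3%, with detection every 8 weeks;
- median 13 or 26 weeks from progression to death;
- 5% or 10% of patients stopping scans at a uniform time in weeks 0-26, with an MRI at stopping;
- a varying share of their later progressions captured off study, dated at the true or scan date.

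| Share captured | Censoring | True 20% reads as | True 3% reads as |
|---|---|---|---|
| 0% | last known alive | 20.7-22.1% | 3.5-4.5% |
| 50% | last known alive | 20.3-21.1% | 3.3-3.7% |
| 90% | last known alive | 19.9-20.3% | 3.0-3.1% |
| 0-50% | last assessment | 19.3-19.9% | 2.8-3.0% |

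With full capture the bias is zero. If captured progressions are dated at the 3-monthly contact, the 50% shifts rise to at most +1.4 and +0.9 points. Over 0-50% capture, 0.9-4.0% of Cohort 1 patients and 0.3-1.8% of Cohort 2 patients are alive at week 26 with undocumented status. That is 0.3-1.4 of 36 and 0.1-0.5 of 29.

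**5. Informative stopping.** If patients stop 0-4 weeks before progression because they are worsening (0-50% capture), last-known-alive censoring gives 20.9-25.2% and 3.9-8.7%. Last-assessment censoring gives 20.3-21.6% and 3.1-3.3%. Counting the unassessed as failures gives 19.8-20.0% and 2.9-3.0%.

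**6. Scale.** One standard error is √(0.2 × 0.8/36) = 6.7 points in Cohort 1 and √(0.03 × 0.97/29) = 3.2 points in Cohort 2.

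**The case against.** **The rule is not written for the primary endpoint.** The sentence stands in the synopsis and the secondary section. Section 13.4.3 could be read as censoring when progression status is lost, and the rule requires the patient to be progression-free as well as alive. This stands in part: applying the rule to the primary PFS6 is an inference. It is a sound one, because the variable and estimator are the same, section 13.5.2 itself lists the 6-month PFS estimate, and no rival date exists.

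**The safeguards are real.** Sections 7.3 and 10.6 seek progression, not only vital status. Section 10.4 keeps MRIs on time during toxicity delays, and sections 10.5 and 10.8.2 ask for final assessments. Section 13.4.3 considers complete 6-month follow-up fully achievable. These narrow the gap, but that assurance concerns clinical status, not imaging. Section 10.4 does not cover permanent removal, and the off-study provisions are conditional.

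**The effect is probably small.** This stands. Of the first 19 patients at 18 mg/kg, section 7.2 accounts for 17: 16 progressed before 6 months and one completed 6 months. The other two are unclassified, not shown to be unscanned. The 50%-capture shifts are well below one standard error.

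**Two stronger readings are not supported.** A reader might infer that the go/no-go error rates are inflated. The count rules do not use the Kaplan-Meier estimate, and how an unassessed patient counts in them is a separate question. A reader might also infer larger shifts, such as 22-24% and 5-7% at 10% stopping. Those figures require every patient who stops to remain alive throughout, which ignores deaths that count as PFS events.

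**Conclusion.** The point holds for the reported PFS6 estimate, its interval and the PFS curve. Followed as written, sections 3.4 and 13.5.2 allow unassessed time to count as progression-free, and section 13.4.3 gives the primary analysis no other date. The direction is upward whenever a patient stops assessment before 6 months, later progresses without this being captured, and is known to be alive.

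The size cannot be taken from the documents. Under 5-10% random stopping and half of later progressions captured, it is about +0.3 to +1.1 points in Cohort 1 and +0.3 to +0.7 in Cohort 2, and it vanishes as capture becomes complete. The per-patient shifts of 1.8 and 3.1 points need no missed-scan rate, but they do assume a constant hazard and a last scan at week 8. The change is worth making because it is cheap and the primary estimate has no control arm. The documents do not show that the bias will be large.

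**What to change.** In sections 3.4 and 13.5.2, and by reference in 13.4.3, state: PFS for patients alive without documented progression is censored at the date of the last adequate MRI-based RANO assessment showing no progression. A visit rated Unable to Assess (Appendix B), a phone contact, or a clinical visit without imaging does not extend the censoring date. Clinical progression and death still count as events. Keep the date last known alive for OS.

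The imaging condition matters. If any documented clinical contact qualified, off-study contacts without scans could bring the same bias back.

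Report two sensitivity analyses of PFS6: (a) censoring at the date last known alive, and (b) counting patients without documented status at 6 months as failures.

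The cost is text in three sections and recording the dates of off-study assessments. Sample size and decision rules do not change. Intervals become slightly wider. Last-assessment censoring is not unbiased either: it is slightly low if stopping is random and still somewhat high if patients stop because they are worsening. The two sensitivity analyses are there to show how much this matters.
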